Best response determination in trials where confirmation of complete or partial response IS NOT required: Best response in these trials is defined as the best response across all time points (for example, a patient who has SD at first assessment, PR at second assessment, and PD on last assessment has a best overall response of PR). When SD is believed to be best response, it must also meet the protocol specified minimum time from baseline. If the minimum time is not met when SD is otherwise the best time point response, the patient's best response depends on the subsequent assessments. For example, a patient who has SD at first assessment, PD at second and does not meet minimum duration for SD, will have a best response of PD. The same patient lost to follow-up after the first SD assessment would be considered not evaluable.

Best response determination in trials where confirmation of complete or partial response IS required: Complete or partial responses may be claimed only if the criteria for each are met at a subsequent time point as specified in the protocol (generally 4 weeks later). See the following table for further information.

Best Overall Response when Confirmation of CR and PR Required

Overall response First time point	Overall response Subsequent time point	Best overall response
CR	CR	CR
CR	PR	SD, PD or PR ^a

CR	SD	SD provided minimum criteria for SD duration met, otherwise, PD
CR	PD	SD provided minimum criteria for SD duration met, otherwise, PD
CR	NE	SD provided minimum criteria for SD duration met, otherwise, NE
PR	CR	PR
PR	PR	PR
PR	SD	SD
PR	PD	SD provided minimum criteria for SD duration met, otherwise, PD
PR	NE	SD provided minimum criteria for SD duration met, otherwise, NE
NE	NE	NE

Note: CR = complete response, PR = partial response, SD = stable disease, PD = progressive disease, and NE = not evaluable. a: If a CR is truly met at first time point, then any disease seen at a subsequent time point, even disease meeting PR criteria relative to baseline, makes the disease PD at that point (since disease must have reappeared after CR). Best response would depend on whether minimum duration for SD was met. However, sometimes 'CR' may be claimed when subsequent scans suggest small lesions were likely still present and in fact the patient had PR, not CR at the first time point. Under these circumstances, the original CR should be changed to PR and the best response is PR.

14.2 Appendix 2 ECOG performance status score

Grade	Performance Status
0	Asymptomatic, fully active, able to carry on all pre-disease activities without restriction.
1	Symptomatic but completely ambulatory, restricted in physically strenuous activity but ambulatory and able to carry out work of a light or sedentary nature. For example, light housework, office work.
2	Symptomatic, ambulatory and capable of all self care but unable to carry out any work activities. Up and about more than 50% of waking hours, < 50% in bed during the day.
3	Symptomatic, capable of only limited self-care, confined to bed or chair 50% or more of waking hours, but not bedbound.
4	Completely disabled, cannot carry on any self-care, bedbound.
5	Death.

References: Am. J. Clin. Oncol.:Oken, M.M., Creech, R.H., Tormey, D.C., Horton, J., Davis, T.E., McFadden, E.T., Carbone, P.P.: Toxicity And Response Criteria Of The Eastern Cooperative Oncology Group. Am J Clin Oncol 5:649-655, 1982.

14.3 Appendix 3 Cockcroft-Gault formula and calculation formula of body surface area

Serum creatinine concentration (mg/dL):

$$\text{Creatinine clearance rate of males (mL/min)} = \frac{(140 - \text{Age}) \times (\text{Body weight})a}{(72) \times (\text{Serum creatinine})}$$

$$\text{Creatinine clearance rate of females (mL/min)} = \frac{(0.85)(140 - \text{Age}) \times (\text{Body weight})a}{(72) \times (\text{Serum creatinine})}$$

Serum creatinine concentration (μmol/L):

$$\text{Creatinine clearance rate of males (mL/min)} = \frac{(140 - \text{Age}) \times (\text{Body weight})a}{(0.81) \times (\text{Serum creatinine})}$$

$$\text{Creatinine clearance rate of females (mL/min)} = \frac{(0.85)(140 - \text{Age}) \times (\text{Body weight})a}{(0.81) \times (\text{Serum creatinine})}$$

^a The unit of age is year and that of body weight is kilogram.

14.4 Appendix 4 Women of child-bearing age and contraceptive measures

Women of child-bearing age refer to any women who have experienced menarche, not experienced surgical sterilization (hysterectomy or bilateral ovariectomy) and not yet reached menopause. Menopause refers to 12-month menostasis of women aged over 45 years in circumstance of lacking other biological or physiological causes. In addition, menopause can be confirmed only serum follicle-stimulating hormone (FSH) level in women aged below 55 years > 40 mIU/mL.

- Women receiving hormone replacement therapy (HRT) may have artificially inhibited FSH levels. Therefore, a wash-out period may be required to reach the physiological FSH level. The duration of wash-out period is associated with the functions of HRT. Wash-out duration recommended by the guideline is as follows. An investigator shall inspect serum FSH level at his or her discretion. If serum FSH level at any time of the whole wash-out period > 40 mIU/ml, the woman will be regarded as menopause:
 - At least one week of using vaginal hormone products (pessulum, ointment, gel)
 - At least four weeks of using transdermal products
 - At least eight weeks of using products for oral administration

Patients (including sexual partners of male patients) of child-bearing potential shall take full contraceptive measures and avoid donating eggs and sperms between the date of signing an informed consent form and month 6 after the last dose. Contraceptive measures acceptable in the study include: absolutely asexual life; intrauterine device (IUDs, e.g. Copper T); cervical cap (adding spermicidal cream or gel) plus male condom; diaphragm (adding spermicidal cream or gel) plus male condom or other two or more contraceptive measures. Patients will be provided with information on relevant acceptable contraceptive measures during patients' informed consent process.

14.5 Appendix 5 New York Heart Association (NYHA) Functional Classification

I	Patients have heart disease, but no limitation of physical activity. Ordinary physical activity does not cause undue fatigue, palpitation, dyspnea or angina pectoris.
II	Patients have heart disease and slight limitation of physical activity. Comfortable at rest. Ordinary physical activity results in undue fatigue, palpitation, dyspnea or angina pectoris.
III	Patients have heart disease leading to marked limitation of physical activity. Comfortable at rest. Less than ordinary activity causes undue fatigue, palpitation, dyspnea or angina pectoris.
IV	Unable to carry on any physical activity without discomfort. Symptoms of heart failure at rest. If any physical activity is undertaken, discomfort increases.

14.6 Appendix 6 QTc Fridericia's formula

$$QTcF = \frac{QT}{\sqrt[4]{RR}}$$

QT refers to the interval from the start of the Q wave to the end of the T wave.

RR refers to the interval from the occurrence of QRS wave group to the occurrence of the next QRS wave.

14.7 Appendix 7 CYP3A4 inhibitor and inducer

CYP3A4 inhibitor	CYP3A4 inducer
Potent:	
 - Anticonvulsants, mood stabilizer - Carbamazepine - Phenytoin (anticonvulsants) - Oxcarbazepine - Barbiturate - Phenobarbital Modafinil - Butalbital Nafcillin - Bosentan Nevirapine - Enzalutamide Primidone - Etravirine Rifabutin - Fosphenytoin Semagacestat - Mephennytoin Talviraline - Methylphenobarbital Thioridazine - Mitotane Vemurafenib - St John's wort (hypericum perforatum) - Bactericide - Rifampicin - Rifabutin - Non-nucleoside reverse transcriptase inhibitor - Efavirenz - Nevirapine - Hypoglycemic agents - Pioglitazone - Troglitazone - Glucocorticoid (glucose increased, immunosuppression) - Modafinil (stimulant)
Intermediate:	
Weak:	

 - Fluoxetine/norfluoxetine - Cimetidine (H₂-antagonist) 	

CYP3A4 inhibitor	CYP3A4 inducer
- Buprenorphine (analgesic) - Cafestol (unfiltered coffee) - Orphenadrine	

Sensitive Substrates of CYP2C8, CYP2C9, and CYP2C19

CYP2C8	CYP2C9	CYP2C19
Repaglinide	Tolbutamide, warfarin	Lansoprazole, omeprazole

14.8 Appendix 8 Examples of P-gp inhibitor

Amiodarone, carvedilol, clarithromycin, dronedarone, itraconazole, lapatinib, lopinavir and ritonavir, propafenone, quinidine, ranolazine, ritonavir, saquinavir and ritonavir, telaprevir, tipranavir and ritonavir, verapamil

Source: <http://www.fda.gov/drug/drug-interactions-labeling>

2.1 Primary

Phase I:

To evaluate the safety and tolerability of HH2710 administered orally in patients with advanced tumors;

To identify the Maximum Tolerated Dose (MTD) and/or Recommended Phase II dose (RP2D).

Phase II:

To evaluate efficacy of HH2710 in patients with advanced tumors with MAPK signaling pathway genetic alterations, at the recommended phase 2 dose (RP2D).

2.2 Secondary

Phase I:

To characterize the pharmacokinetic profile of HH2710 and selected metabolites when administered orally in patients with advanced tumors.

Phase II:

To evaluate the efficacy of HH2710 in advanced tumor patients with MAPK signaling pathway genetic alterations.

To evaluate the safety of HH2710.

2.3 Exploratory

Phase I:

To assess the preliminary efficacy of HH2710.

To explore the changes of the pharmacodynamics (PD) markers of HH2710.

3. Study Overview

3.1 Study Design

This is an open-label, multicenter, first-in-human Phase I/II study which is composed of a Phase I dose escalation stage, phase I dose expansion stage and a Phase II dose extension stage.

3.1.1 Phase I: Dose escalation

The accelerated titration (ATD) incorporated with Bayesian optimal interval (BOIN) design will be used to assess the safety and tolerability, and furthermore, to help find the maximum tolerated dose (MTD), and/or to establish the recommended phase 2 dose (RP2D) combined with data from other sources.

A maximum sample size is 58 patients for the dose escalation (ATD + BOIN). The total number of patients will depend upon the number of dose escalations actually needed.

Accelerated titration part:

One patient per cohort will be assigned to receive HH2710. The first three patients will take HH2710 once daily(QD) in cycle 1 day 1 for the single dose PK testing, from the second day, HH2710 will be administered orally on a continuous twice daily (BID).

The proposed dose level in accelerated titration stage is 25mg, 50mg and 100mg twice daily (BID). It may be adjusted according to the available data.

BOIN design part:

When there is an adverse event of grade ≥ 2 occurs, the dose escalation process will shift to a BOIN design, in which at least 3 patients per treatment cohort will be assigned (ATD + BOIN design details please see Protocol Section 6.2.3)

The provisional dose levels are planned different doses (25mg, 50mg, and 100mg BID, 300mg QD, 400mg (BID/QD), 600mg (BID/QD), and 800mg (BID/QD)) (See details in Protocol Section 6.2.2). Dosing frequency and dose level may be adjusted based on available pharmacokinetic and safety data.

When 800mg QD escalation cohort and 600mg QD expansion cohort suspended due to safety concerns, 300mg QD dose level has been added to explore before or while proceeding with further dose escalation. In addition, an alternative BID dosing regimen starting from 200mg is also reinitiated to better understand the safety, tolerability and PK of HH2710 in dose escalation stage.

After the escalation is completed, select the MTD based on the isotonic regression as specified in [1]. Specifically, select the MTD for which the isotonic estimate of the toxicity rate is closest to the target toxicity rate. If there are ties, select the higher dose level when the isotonic estimate is lower than the target toxicity rate and select the lower dose level when the isotonic estimate is greater than or equal to the target toxicity rate.

Dose expansion stage:

An additional 15 patients per cohort may be included in order to further evaluate the safety, pharmacokinetics and anti-tumor activities among biomarker-selected patients. One or more dose levels may be expanded based on the available data. Patients enrolled could have different tumor types but must be confirmed with specific MAPK pathway genetic alteration (the same requirement as in phase II). The total number of patients will depend upon the number of dose expansions necessary.

3.1.2 Phase II Dose extension:

[figure not shown]
This is an open-label, multicenter, dose extension stage at RP2D to explore the response of patients with particular tumor types harboring MAPK genetic alteration. A maximum of 108 patients will be enrolled.

Patients enrolled will be divided into four cohorts once RP2D is defined and each of them focuses on specific tumors with specific genetic alteration, which NGS (next generation sequencing) will be used to detect, described as follows:

- **Cohort 1:** Patients with *BRAF/NRAS* (mutation sites as follows: *NRAS* G13V, *NRAS* Q61, *BRAF* V600, *BRAF* G469A, L485W, L597Q, T599dup) mutated melanoma;
- **Cohort 2:** Patients with *BRAF/NRAS* (mutation sites as follows: *NRAS* G13V, *NRAS* Q61, *BRAF* V600, *BRAF* G469A, L485W, L597Q, T599dup) mutated non-small cell lung cancer;
- **Cohort 3:** Patients with *BRAF* V600 mutated Langerhans Cell Histiocytosis Syndrome (LCH)/ Erdheim-Chester disease (ECD);
- **Cohort 4:** Patients with RAS/RAF/MEK/ERK mutated tumors that are not included in other cohorts.

The overall study design is described in the following study flow chart.

Figure 1 Study Flow Chart

3.2 Sample Size

Phase I Dose Escalation Stage:

The planned maximum sample size in Phase I dose escalation stage (ATD + BOIN) is 58 including up to 40 subjects for ATD + QD dose escalation cohorts (Part A) and up to 18 subjects for the additional BID dose escalation cohorts (Part B). During the ATD, one-patient per cohort is required for dose escalation. Once the BOIN design starts, cohorts of 3 patients will be used for dose escalation and the maximum number of patients for each dose level should not exceed 15 patients and 12 patients for BOIN design Part A and Part B, respectively.

Phase I Dose Expansion Stage:

We plan to recruit 15 evaluable patients per expansion cohort in the phase I stage of the study. The enrolled patients with different cancers must have confirmation of specific MAPK pathway genetic alteration. The primary focus of the dose expansion is to further assess the safety and pharmacokinetics of HH2710. Preliminary efficacy will also be examined but serve only for an exploratory purpose.

Phase II Dose Extension Stage:

In Phase II, patients will be recruited into the following 4 cohorts at the RP2D level:

Cohort 1: Patients with BRAF/NRAS (mutation sites as follows: NRAS G13V, NRAS Q61, BRAF V600, BRAF G469A, L485W, L597Q, T599dup) mutated melanoma;

Cohort 2: Patients with BRAF/NRAS (mutation sites as follows: NRAS G13V, NRAS Q61, BRAF V600, BRAF G469A, L485W, L597Q, T599dup) mutated non-small cell lung cancer;

Cohort 3: Patients with BRAF V600 mutated Langerhans Cell Histiocytosis Syndrome (LCH)/ Erdheim-Chester disease (ECD);

Cohort 4: Patients with RAS/RAF/MEK/ERK mutated tumors that are not included in other cohorts.

Cohort 1-2 will utilize the Bayesian Optimal design for phase II trials (BOP2). The null hypothesis of the response rate is 0.05, and the alternative hypothesis is 0.16. The design controls the type I error rate at 0.1 and yields the power of 0.8201 under H1.

Table 3-1 Optimized stopping boundaries for cohort 1 and cohort 2 in Phase II

# patients treated	Stop if # responses \leq
23	1
36	3

Based on [Table 3-1](#), we will perform an interim analysis for the first 23 patients. When at least 2 patients experience CR or PR or SD(SD \geq 6 weeks) events, the study will continue recruiting up to 13 more patients in the second stage. When the total number of patients reaches the maximum sample size of 36, we reject the null hypothesis and conclude that the treatment is promising if the number of responses (CR or PR or SD(SD \geq 6 weeks)) are greater than 3; otherwise we conclude that the treatment is not promising.

We plan to recruit a maximum of 9 patients in Cohort 3. Since there are currently no sufficient data available (due to the rarity of the disease), we are unable to calculate the sample size provided for an acceptable statistical justification. However, at this stage, we think that data from 9 patients is considered to be adequate to allow a preliminary investigation of the study objectives for this cohort.

Cohort 4 will include a maximum of 27 patients. Patients included in this cohort will have different cancer types led by different genetic mutations. Thus, it is difficult to calculate sample size for this cohort based on very accurate efficacy goals (e.g. minimum ORR for the alternative hypothesis). Therefore, this cohort serves for an exploratory

purpose and the number of patients has been based on the desire to obtain adequate data whilst exposing as few patients as possible to the study procedures.

4. Study Endpoints and Covariates

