4.1 Study Endpoints

Primary Endpoint

Phase I:

Safety and Tolerability: The incidence, type, and severity of adverse events (AEs) assessed according to the National Cancer Institute-Common Terminology Criteria for Adverse Events (NCI-CTCAE) V5.0, physical examination findings, clinical laboratory values, vital signs and Electrocardiograms (ECGs)

The MTD, if any, and RP2D for HH2710 will be determined based on safety, tolerability, PK, preliminary efficacy, and other available data.

Phase II:

Tumor objective response rate (ORR) based on RECIST version 1.1.

Secondary Endpoints

Phase I:

Peak plasma concentration (Cmax), peak time (tmax), area under the plasma concentration-time curve from time 0 to time (t) (AUC0-t), plasma elimination half-life (t1/2), plasma clearance rate constant (λ_z), apparent clearance (CL/F), apparent volume of distribution (Vz/F).

Phase II:

the duration of response (DoR), progression-free survival (PFS), disease control rate (DCR), time to response (TTR), time to progression (TTP), and 1-year overall survival (OS) rate.

The incidence, type, and severity of adverse events (AEs) assessed according to the National Cancer Institute-Common Terminology Criteria for Adverse Events (NCI-CTCAE) V5.0, physical examination findings, clinical laboratory values, vital signs and Electrocardiograms (ECGs).

Exploratory Endpoints

Phase I:

ORR, DoR, DCR, PFS and TTR.

Changes in PD markers of HH2710 efficacy including phosphorylation of RSK (pRSK) and total RSK.

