4.2 Planned Covariates

No covariates will be accounted for in Phase I (dose-finding and dose expansion). In Phase II (cohort extension), analyses will be analyzed by subgroups of tumor types and/or genetic mutations in order to evaluate the preliminary efficacy.

5. Hypotheses and/or Estimations

Phase I:

No hypothesis for this phase since the primary endpoint are safety profile, MTD and RP2D.

Phase II for Cohort 1 and Cohort 2:

In Cohort 1 and Cohort2, the null hypothesis of the response rate is 0.02, and the alternative hypothesis is 0.16. The design controls the type I error rate at 0.1 and yields the power of 0.8201 under H1.

We will perform an interim analysis for the first 23 patients. When at least 2 patients experience CR or PR or SD (SD \geq 6 weeks) events, the study will continue recruiting up to 13 more patients in the second stage. When the total number of patients reaches the maximum sample size of 36, we reject the null hypothesis and conclude that the treatment is promising if the number of responses (CR or PR or SD(SD \geq 6 weeks)) are greater than 3; otherwise we conclude that the treatment is not promising.

No hypothesis for cohort 3 and cohort 4 of phase II since both cohorts are served as preliminary investigation or exploratory purpose.

6. Analysis Sets

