6.5 Subgroup Analyses

Subgroup analyses will be performed to explore the consistency of the treatment effect when the sample sizes allows for meaningful interpretation. The following subgroup may be used to examine efficacy:

Sex (female vs. male)

Age (<65 vs. ≥ 65)

Race

Tumor type

Genetic mutation

7. Planned Analyses

The HH2710 program is stopped and this study is terminated ahead of time with a limited number of subjects treated than planned. As the result, many planned analyses will have insufficient data to render the planned analyses feasible, meaningful or interpretable. Therefore, many of the planned analyses described in this SAP may not be conducted, depending on data availability or maturity, and purpose of the analysis.

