8.7.1.3 Analysis of Secondary Efficacy Endpoint

If the sample size or the number of responders allow for meaningful interpretation, Kaplan-Meier method will be used to analyze the duration of response (DoR), the progression-free survival (PFS), time to response (TTR) and time to progression (TTP) for each tumor type, genetic mutation and other factors required by sponsor. If possible, a 95% of confidence interval band should be provided for each estimate.

For all the time-to-event endpoints (DoR, PFS, TTR and TTP), the survival curve will be estimated by the Kaplan-Meier estimate, and the first percentile, the median survival, the third percentile and their 95% CI will be provided.

For Time to Response (TTR) and Duration of Response (DoR), only subjects with BOR is CR/PR during the study treatment will be calculated.

DCR and 1-year overall survival (OS) rate will be estimated and analyzed by the same methods as those in ORR.

The listing of all the time-to-event endpoints will be provided.

See Appendix , B, C and E for detailed rule of Censor date for PFS and other time-to-event endpoints.

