8.12 Changes From Protocol-specified Analyses

1 year survival rate instead of 1 year overall survival time will be summarized in SAP.

Percentages will be presented to 1 decimal place unless otherwise specified in SAP.

For baseline characteristics, SAP will present Previous Anti-tumor Therapy Type: medication, surgery and radiotherapy instead of previous chemotherapy and previous immunotherapy.

Updated Safety Set to Safety Analysis Set and All-Treated Set to Full analysis set and keep the algorithm the same as protocol.

Members of the review committee will be internal and external to the sponsor.

Remove “Final Analysis section”. By default, primary analyses are final analysis.

Remove “Percentages will be rounded to the nearest whole number (zeroes are not displayed) with values of “< 1%” and “> 99%” shown as necessary for values falling near the boundaries” from general principles section.

9. Literature Citations / References

Clopper CJ and Pearson ES. The use of confidence or fiducial limits illustrated in the case of the binomial. *Biometrika.* 1934; 26(4):404-413.

Liu S, et al., Bayesian Optimal Interval Designs for Phase I/II Clinical Trials. *Journal of the Royal Statistical Society.* 2015, 64(3): 507-523

10. Appendices

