10.5 Appendix E Definitions

ORR

Objective response rate is defined as the percentage of patients who have at least one confirmed response of CR or PR defined by RECIST 1.1 prior to any evidence of progression.

DoR

Duration of response will be defined as the time from the date of first documented response, (that is subsequently confirmed) until date of documented progression or death in the absence of disease progression, the end of response should coincide with the date of progression or death from any cause used for the PFS endpoint. The time of the initial response will be defined as the latest of the dates contributing towards the first visit response of PR or CR.

DCR

Disease control rate is defined as the proportion of subjects with advanced tumors among whom achieve a best overall response CR/PR/SD after treatment with HH2710.

PFS

PFS is defined as the time from date of first dosing until the date of objective disease progression as defined by RECIST 1.1 or death (by any cause in the absence of progression) regardless of whether the subject withdraws from HH2710 treatment or receives another anticancer therapy prior to progression.

Overall Survival

Overall survival is defined as the interval between the date of first dose and the date of patient death due to any cause. Patients who have not died at the time of the statistical analysis will be censored at the time they were last known to be alive.

TTR

TTR is defined as the duration from the first day of study treatment until the first documented response (CR or PR).

TPP

TPP is defined as the duration from the first day of study treatment until the first documented progression (PD).

Baseline

For data analyses, baseline will be defined as the value measured on day 1 of the start of HH2710. The protocol specifies that all study procedures on day 1 should be completed before the initiation of HH2710 which will be the assumption in the analysis unless the time of the assessment is recorded. If a day 1 value is not available, the latest value before the day of the start of HH2710 may be used.

End of Treatment Date

The end of HH2710 therapy date is the date the decision was made to end investigational product reported on the end of investigational product administration CRF.

End of Study

For a subject: a subject ends the study when they die, consent is withdrawn, or they are lost to follow-up. The end of study date will be captured on the end of study CRF.

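### SAP 3.2 and SAP 5 count stable disease of 6 weeks or more as a response in the Cohort 1 and 2 decision rule, but keep boundaries and error rates set for a 5% versus 16% response rate

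*SAP*

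**What the plan says.** **Hypotheses and boundaries.** SAP 3.2 states: "The null hypothesis of the response rate is 0.05, and the alternative hypothesis is 0.16". It gives type I error 0.1, power 0.8201, and boundaries of stop at 1 or fewer of 23 and not promising at 3 or fewer of 36. Protocol 4.1 and 10.4 derive the same boundaries for a response rate under a Beta(0.05, 0.95) prior. SAP 5 repeats the power and the rule but says "the null hypothesis of the response rate is 0.02, and the alternative hypothesis is 0.16".

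**Event counted in the SAP.** SAP 3.2 and SAP 5 both count CR, PR or SD lasting at least 6 weeks, at the interim and at the final look. The final-look sentence in SAP 3.2 ends "weeks)) are greater than 3; otherwise we conclude that the treatment is not promising".

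**Event counted in the protocol.** Protocol 4.1 and 10.4 admit SD only at the interim, and only if it lasts at least 6 months. At 36 patients they count responses, with no SD added.

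**Primary endpoint.** SAP 4.1 gives "Tumor objective response rate (ORR) based on RECIST version 1.1". SAP Appendix E requires "at least one confirmed response of CR or PR defined by RECIST 1.1". Disease control is a separate secondary endpoint, and SAP 8.7.1.3 says "DCR and 1-year overall survival (OS) rate will be estimated and analyzed by the same methods as those in ORR".

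**Declared changes.** SAP 8.12 lists items such as "1 year survival rate instead of 1 year overall survival time will be summarized in SAP" and the number of decimal places. It mentions neither the move from 6 months to 6 weeks nor the addition of SD to the final test.

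**The concern.** A boundary of 4 events in 36 is demanding when the null event rate is 5%. It is easy to reach when the event is disease control. Protocol 7.2.5 puts the first on-treatment scan at Cycle 3 Day 1 (day 43), and Protocol 7.1 allows a 7-day window either side. SD of at least 6 weeks is therefore close to not having progressed at the first scan. Patients who are not evaluable, or who are scanned early in the window, might not count, but most unprogressed patients would.

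The go/no-go verdict then no longer tests the primary endpoint and no longer has its stated error rates. A cohort could be called promising on stable disease while its ORR sits at the null. The futility look also loses most of its ability to stop an inactive cohort.

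**Working it through.** **Inputs.** p0 = 0.05, p1 = 0.16, boundaries 1/23 and 3/36 (SAP 3.2). Prior Beta(0.05, 0.95), λ = 0.75, α = 0.2 (Protocol 10.4). The documents give no rate of SD of 6 weeks or longer, so every SD rate below is an assumption.

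**Step 1: reproduce the boundaries.** With r events in n patients the posterior is Beta(0.05 + r, 0.95 + n − r). Stop if P(p > 0.05) < 0.75 × (n/36)^0.2.

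| n | Cutoff | Posterior probability at boundary | Posterior probability one event above |
|---|---|---|---|
| 23 | 0.75 × (23/36)^0.2 = 0.6857 | r = 1: 0.327 (stop) | r = 2: 0.695 (go) |
| 36 | 0.75 | r = 3: 0.743 (not promising) | r = 4: 0.902 (promising) |

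The boundaries follow from a null of 0.05.

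**Step 2: reproduce the error rates.** For a counted-event rate p,

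P(promising) = Σ over x = 2 to 23 of P(X₁ = x) × P(X₂ ≥ 4 − x), with X₁ ~ Bin(23, p) and X₂ ~ Bin(13, p).

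- p = 0.05: 0.0936 (stated limit 0.1)
- p = 0.16: 0.8195 (stated 0.8201)

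The stated design is therefore the two-look rule for an event with rates 5% and 16%. A single look at 36 would give 0.1037 and 0.8495.

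**Step 3: apply the SAP's event.** Hold the true CR/PR rate at 5% and add an assumed rate s of SD of 6 weeks or longer, so p = 0.05 + s. The last column is a joint multinomial calculation over CR/PR, SD and neither.

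| Assumed s | Total p | P(stop at 23) | P(promising) | P(promising with 3 or fewer CR/PR in 36) |
|---|---|---|---|---|
| 0 | 5% | 0.68 | 0.094 | 0 |
| 5% | 10% | 0.32 | 0.46 | 0.36 |
| 10% | 15% | 0.12 | 0.78 | 0.67 |
| 15% | 20% | 0.04 | 0.93 | 0.83 |
| 20% | 25% | 0.01 | 0.98 | 0.88 |
| 25% | 30% | 0.003 | 0.996 | 0.89 |

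**Step 4: thresholds that need no assumed SD rate.** Solving P(promising) = c for p gives 5.12% for c = 0.10, 10.5% for c = 0.50 and 18.6% for c = 0.90.

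**Step 5: the protocol's version.** With SD of at least 6 months counted only at the interim and CR/PR at the final look, P(promising) at a 5% ORR is 0.1003 if the total interim-event rate is 10% and 0.1026 if it is 15%. It cannot exceed P(X₃₆ ≥ 4) = 0.1037. Power at a 16% ORR is 0.838 if the interim-event rate is 20%, and at most 0.8495. The cost is weaker early stopping: 0.32 and 0.12 at interim-event rates of 10% and 15%, against 0.68. The large inflation therefore comes from the SAP's final-look wording.

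**Step 6: the null of 0.02 in SAP 5.** At p = 0.02 the same rule gives P(promising) = 0.005, far below the stated 0.1. Rerunning the criterion with p0 = 0.02 and an assumed Beta(0.02, 0.98) prior gives posterior probabilities of 0.493 at r = 1 and 0.843 at r = 2 for n = 36, so the final boundary would be 1, not 3. The 0.02 is a separate error and does not cause the inflation.

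**The case against.** **Impact is limited.** SAP 7 says "this study is terminated ahead of time with a limited number of subjects treated than planned" and that many planned analyses may not be done. The only enrolment the documents report is 26 Phase I patients at 18 January 2022, and they do not show that Phase II opened. The protocol summary calls the study descriptive. All this lowers the practical effect. But SAP 7 does not withdraw the rule, and SAP 5 still states a hypothesis, a rejection criterion, a type I error and a power. Those must match the event counted.

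**The ORR estimate is unaffected.** SAP 8.7.1.2 reports ORR with a Clopper-Pearson interval, and a committee decides whether a cohort continues. A reader would see the true ORR next to a promising verdict. That is correct, but it does not give the verdict its stated error rates.

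**The operating characteristics are not specific to CR/PR.** They hold for any binary event with rates of 5% and 16%. That is so; the link to CR/PR comes from the term response rate and from the ORR definition. Nothing in the documents suggests that disease control has those rates.

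**Six weeks may be a slip for six months.** The protocol writes 6m in one place. If so, the counted SD rate would be lower and the inflation nearer the top rows of the table. SD would still be counted in the final test, which the protocol does not do.

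**The sizes rest on assumed SD rates.** They do. The 5.12% threshold does not.

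**Conclusion.** The concern holds. SAP 3.2 and SAP 5 apply a rule built for a 5% versus 16% response rate to a disease-control event, at both looks, without declaring the change. If only CR/PR counts, the stated design is recovered (0.094 and 0.82). Under the SAP's wording, and with ORR at the null, almost any contribution from SD takes the false-positive probability above 0.10. Adding 10% SD takes it to 0.78, and in most of those cases (0.67 overall) three or fewer of the 36 patients would have responded. The direction needs no outside figure; the size depends on the assumed SD rate. The two documents also disagree on the interim event, and SAP 5 disagrees with SAP 3.2 and the protocol on the null. Early termination reduces the consequence but does not make the written rule valid.

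**What to change.** In SAP 3.2 and SAP 5:

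1. At 36 patients, count only confirmed CR or PR as defined in Appendix E.
2. Remove SD of 6 weeks or longer from the 23-patient count.
3. Change the SAP 5 null from 0.02 to 0.05.
4. Report SD under DCR, which SAP 8.7.1.3 already analyses. Appendix E gives DCR no minimum SD duration, so state one there when the 6-week text is removed.
5. Reconcile the interim event with the protocol. Either use CR/PR only, or keep the protocol's SD of at least 6 months as a lenient futility gate and state its properties: type I error up to 0.104, so the 0.1 claim must be reworded, and less early stopping.

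If a disease-control rule is intended, give it its own null, alternative and boundaries, and list it in SAP 8.12.

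**Cost.** Items 1 to 4 are SAP wording and add no patients. A cohort with only stable disease could then be called not promising. Waiting for confirmation can delay a look by about 6 weeks. CR/PR only at the interim needs a protocol amendment (Protocol 12.1). Keeping the 6-month gate avoids that, but a stop may have to wait until unprogressed patients reach 6 months.
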